1. INTRODUCTION

This document is a protocol for a human research study. The purpose of this protocol is to ensure that this study is to be conducted according to ICH GCP guidelines (CRF 21 Part 312), applicable government regulations and Institutional research policies and procedures.

2. BACKGROUND

2.1 Background Prevalence of Research Topic

AUD is difficult to treat, and currently available medications are underutilized, due at least in part to their limited effectiveness [1-3]. There is a critical need for more efficacious medications for AUD. Preclinical rodent work from ACGT investigator [name] has identified a specific molecular target that promotes excessive alcohol intake. [name] discovered that *collapsin response mediator protein-2 (CRMP-2)* [4], a downstream mediator of *mammalian target of rapamycin complex 1 (mTORC1)* signaling [4-8], is critical for promoting excessive alcohol intake [4].

The central goal of this pilot project is to lay down the groundwork necessary for the later conduct of more definitive studies designed to translate the ACTG's basic science discoveries into human trials of novel pharmacotherapies for AUD. The FDA-approved anticonvulsant, lacosamide [13,38-40] inhibits CRMP-2 [4,12,13]. We will conduct the first pilot laboratory clinical trial of lacosamide in humans with AUD. The ultimate goal of this proposal is that this medication can be repurposed for the treatment of AUD if it is safe and feasible to use in future larger studies that will test its ability to reduce alcohol drinking and behavioral biases for alcohol in heavy drinkers with AUD.

2.2 Prior Experience

2.2.1 Preclinical Experience

CRMP-2 as a novel molecular target for AUD treatment: Studies from [name] groups established that alcohol exposure activates mTORC1 in specific brain regions in rodent, and that mTORC1-related signaling is centrally important for promoting excessive alcohol drinking [4-8]. mTORC1 acts by increasing translation of synaptic plasticity proteins [48], and recent work by [name] group identified one of these proteins, CRMP-2, as critical for promoting excessive alcohol intake [4]. CRMP-2 is a microtubule-binding protein that regulates synaptic structure [4,12,13], and alcohol drinking increases CRMP-2 and microtubule assembly [4]. Importantly, inhibition of CRMP-2 with systemic administration of **lacosamide**, an FDA-approved small molecule inhibitor of CRMP-2 [4,12,13], significantly reduces excessive alcohol intake without altering sucrose intake, open field locomotion or anxiety [4], suggesting that lacosamide does not have more general motor or motivational effects. These exciting findings implicate lacosamide, which is available as the FDA-approved anticonvulsant Vimpat®, as a novel treatment for AUD.

2.2.2 Clinical Experience

Assessing lacosamide effects on alcohol drinking, impulsivity, craving, and approach bias: We will conduct the first human tests of the efficacy of lacosamide to reduce alcohol drinking in non-treatment-seeking heavy drinkers with AUD, using the Yale Alcohol Drinking Paradigm (ADP). The ADP is also referred to as the "O'Malley Choice Against Money Paradigm" in a recent review by Bujarski and Ray [100], who state that the ADP is the more widely used of the two main categories of current oral alcohol-self administration methods. [name] at Yale University helped to develop the ADP, which has been adopted by a number of investigators [16-27], since it has proven highly reliable in measuring medication effects on intake. In addition to alcohol intake, we will also assess whether the test medications are able to *reduce neurobehavioral vulnerabilities* such as *craving, impulsivity, and alcohol approach bias*, that are known to promote heavy alcohol drinking [1,28-34]. We propose to employ measures that are widely used and well-validated. Significant effects by the test medications would indicate that CRMP-2 and/or OXR are also critical to promoting the neurobehavioral vulnerabilities that promote drinking.

3. RATIONAL SIGNIFICANCE

3.1 Problem Statement

Based on findings discussed above, the premise of this work is that (1) molecular mechanisms that drive excessive alcohol intake in rodents can also promote heavy drinking in humans with AUD, that (2) the use of lacosamide, to inhibit CRMP-2 [4,12,13], for reducing human drinking is supported by rodent studies from ACGT researchers and that (3) the Alcohol Drinking Paradigm and the proposed measures of neurobehavioral contributors to alcohol drinking are well-validated and are drivers of alcohol use by heavy drinkers with AUD in human laboratory studies; and that (4) lacosamide may represent a novel and potent pharmacotherapy to treat AUD, which is our overall goal.

3.2 Purpose of Study/Potential Impact

The proposed project will help fulfil the ACGT's goal of translating preclinical findings into clinical trials leading to new pharmacologic approaches to the treatment of alcohol use disorder (AUD).

The goal of the proposed Pilot project is to translate basic science findings from Alcohol Center for Genes and Translation (ACGT) preclinical investigators into clinical research to improve the treatment of alcohol use disorder (AUD). AUD is difficult to treat, and currently available medications are underutilized, due at least in part to their limited effectiveness [1-3]. There is a critical need for more efficacious medications for AUD.

Using preclinical rodent models, ACGT investigator [name] identified the mammalian target of rapamycin complex 1 (mTORC1) [4-8] as a potential drug target for AUD. Lacosamide targets collapsin response mediator protein-2 (CRMP-2) [4,12,13], a downstream mediator of mTORC1 [4]. *We will conduct the first controlled pilot human laboratory study to assess the effects of two doses of lacosamide, versus placebo, on alcohol craving, drinking, and psychomotor effects.*

Based on findings discussed above, the premise of this work is that (1) molecular mechanisms that drive excessive alcohol intake in rodents can also promote heavy drinking in humans with AUD, that (2) the use of lacosamide, to inhibit CRMP-2 [4,12,13], for reducing human drinking is supported by rodent studies from ACGT researchers and that (3) the Alcohol Drinking Paradigm and the proposed measures of neurobehavioral contributors to alcohol drinking are well-validated and are drivers of alcohol use by heavy drinkers with AUD in human laboratory studies; and that (4) lacosamide may represent a novel pharmacotherapy to treat AUD, which is our overall goal. If successful, our experiment will facilitate the development of a new pharmacological strategy for treating human AUD -- inhibition of CRMP-2. In addition, it will provide important scientific information about the salience of CRMP-2 to human heavy drinking and to human behavioral antecedents to drinking.

3.3 Potential Risks and Benefits

3.3.1 Potential Benefits

There is no direct benefit to these participants besides referral to treatment, which will be provided at the end of the study. They will be able to withdraw from the study at any time. The direct benefit is not great for participants, but given the potential benefit to developing effective treatments for alcoholism, the risk-benefit ratio appears favorable.

Participants may benefit somewhat from the extra physical examination, laboratory tests, and attention. In the informed consent form, participants are instructed: "Taking part in this study may not make your health better. If you are in this study, you may benefit from the physical examinations, blood tests, and review of your symptoms. Others may benefit from the overall conclusions drawn from the results of this study."

AUD is major public health problem that contributes prominently to the global burden of disease [58]. While there are several approved medications for the treatment of AUD, the available pharmacotherapies are hampered by small effect sizes, adverse effects, and limited adoption into practice. Currently available FDA-approved pharmacological agents have major limitations and there is a critical need to identify novel medication strategies for AUD treatment. Despite the large numbers of patients who suffer from AUD, medications are greatly underutilized and only a small minority of adults in the United States who have AUD are treated with medications. *This low utilization is thought to be in part due to a perception of AUD medication ineffectiveness.* The potential knowledge to be gained in this study is judged to be highly significant. This research seeks to expand the knowledge base regarding the treatment of alcohol use disorder. Because of the known low to moderate risk profile of the study medications and the close monitoring afforded by the study design, the level of risk for prospective participants is judged to be modest, and therefore, is considered to be reasonable, in comparison with the potential knowledge to be gained.

The results of this laboratory-based drinking paradigm will provide an important initial signal regarding the potential efficacy of lacosamide in reducing alcohol drinking. There is a great need for the development of new agents and combination of agents to treat alcohol use disorder. This laboratory paradigm will also provide information regarding the mechanism of action of these agents and thus significantly contribute to the literature.

3.3.2 Potential Risks and Procedures to Minimize Risks

The major potential risks in this study are related to administration of alcohol, lacosamide, and blood drawing during the physical exam and the alcohol drinking period, and risks to privacy.

Alcohol

A number of medical conditions could potentially be worsened by acute alcohol administration (e.g., liver disease, cardiac abnormality, pancreatitis, diabetes, neurological problems, diabetes, and gastrointestinal disorders). During screening, the study physician will conduct a medical history and physical exam and review laboratory findings. As a result, participants with medical problems that are judged by the study physician/PI ([name]) will be excluded from the study.

Alcohol may also cause nausea in high doses; however, nausea is not expected at the dose being used in this sample of heavy drinkers. Participants will not be drinking to levels more than they typically consume in their own drinking context, and, with the exception of the priming dose, they determine the amount of alcohol consumed.

Another area of potential risk to participants under the influence of alcohol involves their safety during the experimental procedures. Although impairment of gross motor coordination in heavy drinkers is rare at the alcohol dose used in this study, all participants will be under the supervision of the experimenters to prevent possible accidents such as falls. Participants will not leave the laboratory during the self-administration procedure,

Alcohol is a reinforcing agent, which may cause changes in behavior including repetitive or excessive alcohol consumption. Because of this, the administration of alcohol to alcoholics in treatment could potentially impede the progress of their recovery. In addition, the administration of alcohol to sober alcoholics living in the community presents a possible risk of relapse. As a result, we will be recruiting non-abstinent non-treatment-seeking alcoholics in keeping with the National Advisory Council on Alcohol Abuse and Alcoholism's recent update of its 1989⁴¹ recommended guidelines on ethyl alcohol administration. At completion of the study, we will make a serious and concerted effort to link the participant with treatment for their alcohol problems. This will be done by giving the participant objective feedback about the fact that their drinking exceeds standards for avoiding hazardous drinking, providing a brief one-session motivational intervention for their drinking, and by arranging for alcohol treatment services if they are interested. In our previous and ongoing work, several participants quit drinking and many others reduced their drinking in the three months following this intervention.

****Protection against risks of alcohol challenges****

The alcohol challenges will be conducted by [name] and research staff, using methodology adopted from the Yale group, and trained by our Yale colleague, [name].

We provide a number of safeguards to reduce the risk of physical injury by supervising all sessions and having participants stay in the CRC until they are alert and do not show signs of psychomotor impairment. We also exclude participants for whom physical or psychological problems contraindicate alcohol consumption. By selecting non-treatment-seeking participants who are currently drinking heavily on a regular basis, we are not exposing participants to alcohol consumption levels that differ from their normal drinking context. Although this has not happened in the Yale group's experience, should a participant insist on leaving the research setting prematurely, we will provide transportation back to their residence. This contingency will be explicitly addressed in the consent form.

Clearly, participants are free to discontinue the experiment at any time, although we would strongly encourage them to remain in the research setting until their blood alcohol level is below .02 and alertness and psychomotor status are judged to be safe.

Because participants are not in treatment, participation in an alcohol challenge study will not interfere with efforts to achieve abstinence. At the end of the study, however, a potential benefit is that participants will be provided with a professional evaluation and treatment will be arranged if they express interest.

****Protection against the risk of heavier alcohol use, suicidality, or other medical or psychiatric problems that may arise over the course of the study****

To protect against this risk, we will do the following:

-We will closely monitor alcohol use at each visit.

-Participants will be withdrawn from the study if, in the opinion of the PI or the DSMB, there is: sustained clinically significant increase in alcohol use between ADP sessions 1, 2 and 3, suicidal ideation consisting of suicidal intent or plan, unacceptable

adverse events judged by the study physician (the PI, [name]) to be related to study interventions, or any other clinically significant medical, psychiatric, or substance use related poor outcome that makes continued study participation unsafe.

Blood and Urine Collections

Screening blood and urine collections are performed primarily as safeguards to participants and should add no risks other than those normally associated with these procedures. Participants will have approximately 40 cc of blood drawn at the intake appointment to determine liver and kidney functioning, and during the self-administration portions of the study we will draw approximately 20 cc of blood at each of the 3 visits. Therefore, the total amount of blood drawn during the study (100 ml) poses minimal risk in healthy participants. We will advise participants against donating blood for six weeks following study participation.

Risk of Study Medication - Lacosamide

Adverse effects

The 10 most common adverse effects associated with lacosamide 200 mg/day (100 mg twice per day) when used as *adjunctive therapy* in patients with partial-onset seizures (placebo comparison in parentheses) were: dizziness 16% (8%); headache 11% (9%); nausea 7% (4%); fatigue 7% (6%); vomiting 6% (3%); diplopia 6% (2%); vomiting 6% (3%); vertigo 5% (1%); somnolence 5% (5%); tremor 4% (4%); ataxia 4% (2%)¹³.

Relevant Warnings/ Precautions in FDA-approved Package Insert for Lacosamide (Vimpat®)

Suicidality associated with anticonvulsants

Even though participants will be exposed to only a single dose of lacosamide, it has been noted that "all antiepileptic drugs including lacosamide increase the risk of these thoughts or behaviors in patients taking these drugs for any indication"¹³. An FDA Alert, updated 12/16/2008, (US Food and Drug Administration 2008) 11 antiepileptic or anticonvulsant drugs associated with: "reports of suicidality (suicidal behavior or ideation [thoughts])...FDA is requiring ... that all manufacturers of drugs in this class include a Warning in their labeling.... FDA's pooled analyses of 199 clinical trials of eleven antiepileptic drugs... showed that patients who received one of the antiepileptic drugs had almost twice the risk of suicidal behavior or ideation (0.43%) compared to patients who received placebo (0.24%). This... represents the occurrence of approximately one additional case of suicidal thinking or behavior for every 530 patients treated with an antiepileptic drug... The increased risk was observed as early as one week after starting treatment and throughout the observed duration of treatment. The increased risk of suicidal thoughts or behavior was generally consistent among the eleven drugs with varying mechanisms of action and across a range of indications. This observation suggests that the risk applies to all antiepileptic drugs used for any indication...."

Dizziness and ataxia

The package insert notes this as a warning/precaution¹³. See above for incidence of these adverse effects. At the doses that we will be using, dizziness and ataxia could be expected to occur in 16% and 4% of participants, respectively, and may be increased by combining lacosamide with alcohol.

Cardiac rhythm and conduction abnormalities

The package insert notes this as a warning/precaution¹³. It is recommended that an ECG be obtained before starting lacosamide and that other medications that could prolong PR interval be avoided.

Syncope

Although listed as a warning/precaution¹³, the package insert notes that there was no increase in syncope compared to placebo in epilepsy patients with no significant system illnesses.

Controlled substance

Lacosamide is schedule V controlled substance, indicating a potential for human abuse that is the lowest among the 5 schedules of controlled substances. In a human abuse potential study, single doses of 200 mg and 800 mg of Lacosamide produced euphoria-type subjective responses¹³. At therapeutic doses, the rate of euphoria reported as an adverse effect was less than 1%¹³. No withdrawal syndromes have been reported.

Interactions of Lacosamide and Alcohol

There are no published reports of lacosamide-alcohol pharmacokinetic (PK) or pharmacodynamics interactions. It is reasonable to assume that there may be additive effects of the combination of lacosamide 100mg with alcohol. Possible risks may include added sedation and added psychomotor impairment that could persist for several hours after last alcohol self-administration (2:00-3:00 PM). It is expected that alcohol effects will wear off in the ensuing 5 hours before discharge from the CRC at 8:00 PM. Tests of alertness and gait/body sway will be administered throughout the testing day to monitor these effects.

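### Scheduled discharge after each lab session has no binding alcohol level: release rests on clinical status and a planned 8:00 PM leaving time

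*Combined protocol and SAP*

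**What the plan says.** Section 3.3.2, under protection against risks of alcohol challenges, describes supervised sessions and "having participants stay in the CRC until they are alert and do not show signs of psychomotor impairment". A later sentence says that participants may discontinue at any time, and adds: "we would strongly encourage them to remain in the research setting until their blood alcohol level is below .02". That sentence also asks that alertness and psychomotor status be judged safe. For early leavers, "should a participant insist on leaving the research setting prematurely, we will provide transportation back to their residence".

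The subsection of 3.3.2 on interactions of lacosamide and alcohol gives the timetable: "It is expected that alcohol effects will wear off in the ensuing 5 hours before discharge from the CRC at 8:00 PM". It says that no lacosamide-alcohol interaction reports have been published, and that additive sedation and psychomotor impairment could persist for several hours after the last drink. It continues: "Tests of alertness and gait/body sway will be administered throughout the testing day to monitor these effects". The dizziness and ataxia subsection says that these effects "may be increased by combining lacosamide with alcohol". Section 6.1.1 repeats that there are no published human data on the combination.

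Section 6.3.5 lists breath alcohol, blood alcohol and a physician's gait and body sway check for the lab sessions. It ties no alcohol value to release.

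**The concern.** The advisory sentence asks for two things before a man leaves: a level below .02, and safe alertness and psychomotor status. The sentence that governs routine release carries only the second. A man can therefore meet the written release condition while above the one alcohol level that the protocol names.

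Clinical checks alone are a weak guide to residual alcohol in this population. Section 3.3.2 itself says that gross motor impairment is rare in heavy drinkers at the dose used, so a normal gait says little about how much alcohol remains. No pass mark is given for the alertness or gait tests.

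Safety of lacosamide with self-administered alcohol is a primary aim (section 4.2), and so is fine-tuning these procedures for later work. A release rule is something this pilot should settle.

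**Working it through.** **The plan's own interval.** Last self-administration is at 2:00 to 3:00 PM and discharge at 8:00 PM: 20:00 − 15:00 = 5 h (6 h from 2:00 PM). The stated 5 hours reproduces. Whether it is long enough depends on the amount drunk.

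**Release conditions side by side.**
- Leaving on schedule: alert, no signs of psychomotor impairment, planned for 8:00 PM. No alcohol value.
- Wishing to discontinue: encouraged to stay until below .02 and clinically safe. Not binding, because volunteers cannot be held.
- Insisting on leaving early: transport home.

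**When would a man still be at or above .02 at 8:00 PM?**

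Inputs from the protocol: the .02 level; 8:00 PM; 8 drinks offered per session (section 6.3.5, consistent with 8 × $3 = $24); one priming drink (section 5.1).

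Assumed inputs: .02 is in g/dL; weight 80 kg; distribution factor 0.68; 14 g alcohol per standard drink; first drink at 11:00, so 9 h of elimination by 8:00 PM; elimination rate b from 0.012 to 0.025 g/dL per hour; priming drink the same size as the others.

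Distribution volume = 80 × 0.68 × 10 = 544 dL. Level at 8:00 PM = grams/544 − 9b, not below 0. The session total that gives exactly .02 is N = (0.02 + 9b) × 544/14. Nine standard drinks are 126 g (126/544 = 0.232); nine half-size drinks are 63 g (63/544 = 0.116). Extra wait to reach .02 = (level − 0.02)/b.

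| b | N, standard drinks | Level, nine standard | Extra wait, nine standard | Level, nine half-size |
|---|---|---|---|---|
| 0.012 | 4.97 | 0.124 | 8.6 h | 0.008 |
| 0.015 | 6.02 | 0.097 | 5.1 h | 0 |
| 0.020 | 7.77 | 0.052 | 1.6 h | 0 |
| 0.025 | 9.52 | 0.007 | 0 h | 0 |

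**Sensitivity of N.** First drink at 12:00 (8 h): 4.5 to 8.5. At 70 kg and 9 h: 4.4 to 8.3. At 100 kg and 9 h: 6.2 to 11.9. Nine half-size drinks equal 4.5 standard drinks, so they reach .02 only at the edge of these ranges. For example, at 70 kg with the slowest elimination, 63/476 − 0.108 = 0.024.

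**The case against.** The strongest reply is that release is already conditional. Men stay until they are clinically fit, and nothing says that 8:00 PM overrides this. There is a physician's gait check, alertness testing, physician review at each visit, five to six hours of observation after drinking and a call the next day. For an unknown interaction, functional tests can detect combined impairment, which a breath reading cannot. The .02 sentence might also be meant as the general standard, worded as encouragement because volunteers cannot be detained. All of this lowers the risk and is a reason to keep the functional tests. It does not make any alcohol level a condition of routine release.

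The source is also incomplete. The sentence in 3.3.2 on not leaving the laboratory during self-administration breaks off at a comma. The session timing table and the consent pages are not in the supplied text. A discharge reading may already be scheduled, but a reading is not a release rule.

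Some stronger readings are tempting and should not be drawn:
- **Release rests on appearance alone.** It does not; tests and physician review are planned.
- **No human data exist.** The documents say only that none are published.
- **The remaining lacosamide is itself hazardous at discharge.** With the stated 13-hour half-life, 0.5^(11.5/13) = 0.54 of the 8:30 dose remains, but the documents link that amount to no risk threshold.
- **Men will be taken above their usual drinking.** Section 3.3.2 says "Participants will not be drinking to levels more than they typically consume in their own drinking context", while entry is set by a weekly average (25 to 70 drinks). Apart from the priming drink, intake is self-determined, each declined drink pays $3, and drink size is not given. A weekly average also does not give a man's usual maximum. The documents do not show the assurance to be false.

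**Conclusion.** The point holds in a limited form. In the supplied text, scheduled discharge depends on clinical status and a planned leaving time, and .02 is advisory only. A man could be released under the plan while above the level that the protocol itself names.

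How often this would happen cannot be determined. On the 80 kg assumptions it needs a session total above about 5.0 to 9.5 standard drinks. Eight drinks plus priming give anything from 0 to 0.124 g/dL at 8:00 PM, depending on whether they are half or full size and on elimination rate. A reader might infer that men will be sent home above .02; the documents do not support that, because drink size is unstated and intake is voluntary. The gap in the rule does not depend on these figures. This is a change that should be made, given the lack of published interaction data, but the existing safeguards mean that it does not invalidate the study.

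**What to change.** In all three sessions, make routine discharge require a breath alcohol reading below .02 and normal gait and alertness checks. Set 8:00 PM as the earliest time, and repeat the reading until it passes. Name all three sessions explicitly, because parts of section 6.3.5 mention only sessions 1 and 2 for alcohol measures. Keep the present handling for anyone who will not wait: encouragement to stay, and transport home.

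The cost is a short amendment, a consent line that a session may exceed 12 hours, and a breath reading at discharge if none is scheduled. The device and the checks are already in use. Four completers with three sessions each make 12 completed sessions. On the 80 kg figures the extra stay is nil with half-size drinks, and 0 to 8.6 hours for a man who takes nine standard drinks. Drinking ends by 3:00 PM, so the drinking data from the session are unaffected.
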